#### **12.2.1.2. Serious Adverse Event**

An SAE is an AE occurring during any trial phase (ie, screening, treatment, or follow-up), and at any dose of the investigational product, that fulfils one or more of the following:

- Results in death
- It is immediately life-threatening
- It requires inpatient hospitalization or prolongation of existing hospitalization
- It results in persistent or significant disability or incapacity
- Results in a congenital abnormality or birth defect
- It is an important medical event that may jeopardize the subject or may require medical intervention to prevent one of the outcomes listed above.

The time period for collecting and documenting SAEs for each subject begins from the time the subject provides informed consent through the end of study (EOS) or early discontinuation from the study. For this study, the reporting of CRS and/or ICANS/Neurotoxicity events will follow the SAE timelines and reporting requirements.

#### **12.2.1.3. Reactogenicity to the Vaccine**

Injection site reactions, skin rash, and pruritis will not be considered a DLT or safety event and should be recorded in the patient diary and eCRF for reactogenicity. (See [Section 6.7.3](#) for DLT

Guidelines, [Section 6.8.5](#) for toxicity management, and [Section 12.2.1.2](#) for SAE definition.) Severe skin rashes such as Steven-Johnson Syndrome or toxic epidermal necrolysis (TEN) will be considered a DLT and should be reported on the eCRF as safety events including SAE as appropriate. Reactogenicity monitoring will include subject's reactogenicity to the trial drug (vaccine). This will be captured at several time points as follows:

- 1-hour post ELI-002 dose administration (subjects will be observed in the clinic for at least 1-hour after each dose)
- 1-week post ELI-002 dose administration (subjects will record daily observations in diary)
- Any unresolved reactogenicity event should be followed until resolution.

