Likewise, 5 subjects with advanced pancreatic cancer were treated with synthetic RAS peptides used as a cancer vaccine. All subjects were vaccinated at Day 0, and booster vaccinations were performed similarly on Days 7-10 and at 1 month. Further booster vaccinations were performed at 4-6-week intervals or as long as the subject's immunological response and overall performance status permitted over a period of 2 to 10 months. The treatment was well tolerated and could be repeated multiple times in the same subject. No sign of toxicity and no adverse events (AEs) were observed [Gjertsen et al, 1996].

ELI-002 is expected to elicit common side effects often associated with vaccines such as local skin reaction, fever, fatigue, pain, among others which generally subside within a day or two. Reactogenicity refers to a subset of reactions that occur soon after vaccination and are a physical manifestation of the inflammatory response to vaccination. In clinical trials, information on expected signs and symptoms after vaccination is actively sought (or 'solicited'). These symptoms may include pain, redness, swelling or induration for injected vaccines, and systemic symptoms, such as fever, myalgia, headache, or rash. The broader term "safety" profile refers to all AEs that could potentially be caused/triggered or worsened at any time after vaccination, and includes AEs, such as anaphylactic reactions, diseases diagnosed after vaccination and autoimmune events.

The administration of 48 µg Peptide with either 5 or 25 µg Adjuvant was well tolerated in the rodent Study No. 2795-002 with a dose-dependent reduced incidence and severity of local irritation and limited associated effects. Therefore, the NOAEL was 48 µg Amph-Peptides/25 µg Adjuvant. Local reactions were considered adverse at the high adjuvant Amph-CpG-7909 dose in the GLP toxicity study which confirms the importance of reactogenicity monitoring. Local

reactions and some flu-like symptoms are expected in subjects who receive peptide injections, and there is always a possibility of hypersensitivity reactions. Injection site reaction is the only AE known to be attributed to ELI-002. Reactogenicity monitoring will occur throughout the ELI-002-001 trial (see [Section 12.2.1.3](#))

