## **12.2. Adverse and Serious Adverse Events**

### **12.2.1. Definition of Adverse Events**

#### **12.2.1.1. Adverse Event**

An AE is the development of an undesirable medical condition or the deterioration of a pre-existing medical condition following or during exposure to a pharmaceutical product, whether or not considered study-drug related. An AE can be any unfavorable and unintended sign, symptom of disease temporally associated with the use of study drug, without any judgement about causality (see current ICH guidelines).

In this study, investigators should report AEs based on CTCAE v5.0 criteria, or ASTCT consensus criteria in the event of either CRS or immune effector cell associated neurotoxicity

syndrome (ICANS). Treatment-emergent AEs (TEAEs) are defined as events not present prior to the initiation of study drug or any event already present that worsens in either intensity or frequency following exposure to study treatment. AEs must be recorded in the eCRF and on forms as provided by Elicio.

An AE does not include the following:

- Medical or surgical procedures (eg, surgery, endoscopy, dental extraction, transfusion); the condition that necessitates the procedure is the AE
- Any pre-existing disease or condition, or laboratory or ECG abnormality, which is present prior to the start of the study medication and that does not worsen
- Laboratory or ECG abnormalities without clinical significance (ie, those which do not require medical intervention or that do not result in discontinuation or interruption of the study drug)
- Situations where an adverse medical event has not occurred (ie, hospitalization for elective surgery, social admission)
- Overdose of study medication or any concomitant medication without any signs or symptoms, unless the subject is hospitalized for observation

The time period for collecting and documenting AEs for each subject begins from the time the subject is administered the first dose of study drug through end of treatment (EOT) or early discontinuation of treatment.

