## 12.5. Recording Adverse Events

Adverse events spontaneously reported by the subject and/or in response to an open question from the trial personnel or revealed by observation will be recorded during the trial at the investigational trial center. Treatment emergent AEs (TEAEs) are defined as events not present prior to the initiation of study drug or any event already present that worsens in either intensity or frequency following exposure to study treatment. AEs must be recorded in the eCRF and on forms as provided by Elicio. The AE term should be reported in standard medical terminology when possible. For each AE, the investigator will evaluate and report the onset (date and time), resolution (date and time), severity, causality, action taken, outcome, and whether or not it caused the subject to discontinue the trial.

Severity will be assessed according to CTCAE or ASTCT as appropriate for the event. For AEs not described in the consensus criteria, the following scale will be used:

- Mild (awareness of sign or symptom, but easily tolerated. Concomitant prescription medications are not ordinarily needed for relief of symptoms)
- Moderate (discomfort sufficient to cause interference with normal activities. Concomitant prescription medications/treatment(s) may be needed for relief of symptoms)
- Severe (incapacitating, with inability to perform normal activities. Requires interruption or discontinuation of study medication. Systemic drug therapy or other treatment is needed)

Reactogenicity will be assessed according to the toxicity grading scale for local reactions for preventive vaccines (see [Section 12.2.1.3](#)).

It is important to distinguish between serious and severe AEs. Severity is a measure of intensity whereas seriousness is defined by the criteria under [Section 12.2.1.2](#). An AE of severe intensity may not be considered serious.

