### 13.7.1 Adverse events

All Adverse events (AEs) will be classified by Primary System Organ Class (SOC) and Preferred Term (PT) according to the Medical Dictionary for Regulatory Activities (MedDRA) Version 23.1 or higher.

**Final Analysis  
Statistical Analysis Plan (SAP)**

AEs will be graded according to the National Cancer Institute Common Terminology Criteria for Adverse Events (NCI CTCAE) version 5.0. For CRS/ICANs (Immune effector Cell-Associated Neurotoxicity syndrome), AEs will be graded according to the American Society for Transplantation and Cellular Therapy (ASTCT) criteria.

In summaries by SOC and PT, the SOC terms will be presented alphabetically, and PTs within each SOC will be sorted by decreasing frequency within the overall column. In summaries by PT, AEs will be sorted by decreasing frequency in the overall column.

**TEAE:** any events not present prior to the initiation of study treatment or any event already present that worsens in either intensity or frequency following exposure to study treatment. Details for imputing missing or partial start dates of adverse events are described in Section 7.3.1.

AE summary tables will be presented for the following categories using counts and percentage of subjects (i.e., number and percentage of subjects with an event):

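### Protocol 12.2.1.3 takes injection site reactions, rash and pruritus out of the safety events, 12.2.1.1 and 4.6.3 do not, and the SAP does not say whether they count in the TEAE rates

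*Protocol*

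**What the plan says.** The first safety measure among the primary endpoints is the incidence of AEs (Protocol 6.2.1, SAP 9.1.1).

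Protocol 12.2.1.3 says: "Injection site reactions, skin rash, and pruritis will not be considered a DLT or safety event". Such events "should be recorded in the patient diary and eCRF for reactogenicity". One group is brought back: "Severe skin rashes such as Steven-Johnson Syndrome or toxic epidermal necrolysis (TEN) will be considered a DLT", and these are to be reported as safety events. Capture is at 1 hour and daily for one week after each dose, and unresolved events are followed until they resolve.

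Protocol 12.2.1.1 is broader: "An AE can be any unfavorable and unintended sign, symptom of disease temporally associated with the use of study drug". Its list of what is not an AE does not name injection site reactions, rash or pruritus. Protocol 4.6.3 states: "Injection site reaction is the only AE known to be attributed to ELI-002". It also says that the safety "profile refers to all AEs that could potentially be caused/triggered or worsened at any time after vaccination".

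Grading differs too. Protocol 12.2.1.1 and SAP 13.7.1 use CTCAE v5.0 for AEs. Protocol 12.5 says: "Reactogenicity will be assessed according to the toxicity grading scale for local reactions for preventive vaccines". For that scale it points to 12.2.1.3, which contains none.

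SAP 13.7.1 defines a TEAE as "any events not present prior to the initiation of study treatment or any event already present that worsens", with no exception for reactogenicity. Its table of planned AE summaries lists reactogenicity as an AE type. That row is marked for the overall TEAE summary, left blank for SOC and PT, and given a separate summary by type, event and grade.

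**The concern.** Two programmers could follow the documents faithfully and produce different primary safety tables. One would take the definitions in 12.2.1.1 and SAP 13.7.1 and count every injection site reaction, rash and pruritus as a TEAE. The other would take 12.2.1.3, treat them as outside safety, and report them only as reactogenicity.

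The related-TEAE rate is the most exposed, because the one AE that 4.6.3 attributes to the product may be in or out. Dose escalation also rests on treatment-emergent AEs (Protocol 6.1.1, SAP 8.1), and in the GLP mouse study the adverse findings at the high adjuvant dose arose from local toxicity at the injection site (Protocol 4.4.1.2). A comparison of local reactions across dose levels should not depend on which section a reader follows.

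A second question is capture. Protocol 12.2.1.3 gives no onset limit in its exclusion sentence, while the diary lasts only 7 days per dose. A rash or pruritus that begins later could be seen as neither a safety event nor a diary entry.

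**Working it through.** The documents give no AE rate for these events, so there is no planned figure to reproduce.

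**Effect on incidence.** Reclassifying one subject whose only events are of these types changes incidence by 1/n:

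- cohort of 3: 1/3 = 33.3 points
- cohort of 6: 1/6 = 16.7 points
- planned total of 18 (Protocol 13.1): 1/18 = 5.6 points

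Illustration only, on an assumption: suppose all 18 subjects have at least one event, and 3, 6 or 12 of them have only these types. Incidence is 100% when they are counted. When they are not, it is 15/18 = 83.3%, 12/18 = 66.7% or 6/18 = 33.3%.

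In the SOC/PT tables, every subject with such an event changes the row concerned, whether or not the subject has other AEs.

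**Diary coverage.** Inputs are the scheduled dose days 57, 64, 71, 78, 92, 106, 196, 203, 210 and 217 (Protocol Tables 12 and 14) and a 7-day diary, with the dose day taken as diary day 1. The end of AE collection differs between sections: end of treatment in 12.2.1.1 (Day 217), and 30 days later in 12.7 (Day 247).

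- Covered to Day 247: Days 57–84 (28), 92–98 (7), 106–112 (7) and 196–223 (28), so 28 + 7 + 7 + 28 = 70.
- Window to Day 247: 247 − 57 + 1 = 191 days. Uncovered: 191 − 70 = 121, or 63%. The gaps are Days 85–91, 99–105, 113–195 and 224–247 (7 + 7 + 83 + 24 = 121).
- Window to Day 217: 217 − 57 + 1 = 161 days. Covered: 28 + 7 + 7 + 22 = 64. Uncovered: 97, or 60%.
- The 28 days from first dose (Days 57–84) are fully covered.

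If the diary starts the day after dosing, 121 days to Day 247 and 98 days to Day 217 are uncovered. The longest gap stays at 83 days.

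**The case against.** The best defence is that 12.2.1.3 should be read under its own title. Protocol 4.6.3 describes reactogenicity as reactions that occur soon after vaccination. On that reading, a rash that starts weeks after a dose is not reactogenicity but an ordinary AE under 12.2.1.1. Each no-dosing visit (Visits 9 to 11) asks for AEs since the last visit and includes a physical examination. Events inside the window are recorded and followed to resolution. Reporting solicited reactions separately is a familiar vaccine-trial convention, and the SAP adds a by-subject listing. Protocol 4.6.3 also expects fever, fatigue, myalgia and headache, which 12.2.1.3 does not remove, so many subjects might count in the any-TEAE rate either way.

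Much of this stands, and it rules out three stronger inferences:

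- *Late skin events will be lost.* The visits ask for AEs, so this is a risk at a site that reads 12.2.1.3 literally, not a consequence of the plan.
- *The 5.0-week median for skin toxicity in 4.6.5 shows that events will fall in a gap.* It concerns a checkpoint inhibitor in metastatic melanoma. Five weeks after first dose is Day 57 + 35 = Day 92, the day of Dose 5, which a diary covers.
- *The total shift in the TEAE rate can be stated.* That needs the share of subjects with such reactions and the share of those with no other AE. The documents give neither.

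The defence does not settle classification. Even for events inside the window, 12.2.1.3 conflicts with 12.2.1.1 and 4.6.3. A reactogenicity row in the overall summary does not say whether those events also enter the any-TEAE and related-TEAE rows or the SOC/PT tables.

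**Conclusion.** The inconsistency is real and touches a primary endpoint. For events inside the diary window it is a matter of classification and grading scale, not of loss. The size is 33.3, 16.7 or 5.6 points per affected subject at n = 3, 6 or 18. These figures need no assumed rate, but the number of affected subjects is unknown before the data are seen.

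The capture risk is secondary. It rests on a site applying 12.2.1.3 beyond its heading, in the 121 of 191 days (or 97 of 161) without a diary.

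The safety tables are descriptive and no test depends on them, so the change should be made for clear reporting. The same sentence in 12.2.1.3 also says that these events are not DLTs, while 6.7.3 lists certain Grade 3 or higher rashes as DLTs. Those passages must be reconciled separately, and this point does not depend on the outcome.

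**What to change.** In Protocol 12.2.1.3, delete the words *or safety event* and state that injection site reactions, rash and pruritus are AEs. State that those within the 7-day diary go on the reactogenicity eCRF and those with later onset go on the AE eCRF. Reconcile the local-reaction scale in 12.5 with CTCAE in 12.2.1.1, and supply the scale that 12.5 refers to.

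In SAP 13.7.1, tabulate any-TEAE, related-TEAE and SOC/PT incidence including the solicited reactions from the reactogenicity eCRF, and again excluding them, with the grading scale shown on each table.

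The cost is a protocol clarification, one extra set of tables, some mapping of reactogenicity terms to SOC and PT, and some added AE entry at sites. The synopsis plans the last enrolment for 2Q2023 and SAP 14.0 records early termination of long-term follow-up, so the protocol edit may come too late to change collection. The SAP change uses data already on the eCRF and still works at final analysis.

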## **6.7. Management of Study Drug-Related Events**

### **6.7.1. Temporarily Suspending Treatment Administration**

If a subject meets any of the following conditions within 48 hours prior to the scheduled administration of the trial treatment, treatment administration will be temporarily suspended:

1. To reduce the risk of CRS, subjects will not be given a repeat dose of ELI-002 if they are exhibiting  $T \geq 38^{\circ}\text{C}$  and/or  $\text{IL-6} \geq 500 \text{ pg/mL}$  (cytokine collection, including IL-6, may be performed up to 7 days prior to treatment). In addition, if a subject exhibits  $\text{IFN}\gamma \geq 1000 \text{ pg/mL}$ , the Elicio medical monitor should be contacted for consultation.
2. Adverse event(s) that meet the definition of DLT caused by prior treatment. See [Section 6.7.3](#) for the definition of a DLT; see [Section 12.4](#) for the definition of Common Terminology Criteria for Adverse Events (CTCAEs).
3. Any subsequent dosing in a subject who has experienced Grade  $\geq 2$  CRS/ immune effector cell-associated neurotoxicity syndrome (ICANS)

Investigators must consult the medical monitor to discuss any subjects meeting the above criteria.

In the event the ELI-002 dose is held, the subject should not receive any make up dose and remain on the original protocol schedule (ie, their next dose will be at the next protocol-specified dose if they meet the criteria for dosing). All trial procedures and treatment administration will be resumed as soon as the subject's condition allows or at the investigator's discretion after Sponsor approval.

The trial may proceed at a lower dose, at a less frequent schedule, or omitting the Amph-CpG-7909 adjuvant while continuing to administer the Amph-Peptides, based on emerging toxicity or pharmacodynamic data until the MTD is determined.

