### 6.7.3. Dose-limiting Toxicity Guidelines

A DLT will be defined as any event at least possibly related to ELI-002 as follows:

- a. Any Grade  $\geq 3$  non-hematologic toxicity except asymptomatic laboratory abnormalities (see Section 12.2.1.1)
- b. Any Grade  $\geq 3$  toxicity involving major organ systems for greater than 72 hours and occurring within 28 days of subcutaneous administration
- c. Grade 3 CRS that does not resolve to  $\leq$  Grade 2 within 7 days
- d. Any Grade 4 CRS that does not improve to  $<$  Grade 2 within 72 hours
- e. Any Grade  $\geq 3$  autoimmune disorder
- f. Any Grade  $\geq 3$  rash that does not resolve to  $\leq$  Grade 1 within 7 days with appropriate treatment

The DLT observation period will be 28 days.

Maximum tolerated dose definition: The MTD is defined as the highest dose level with a DLT incidence  $<33\%$  of cohort subjects.

See protocol Section 6.7.1 and Section 6.8 for management of toxicity.

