#### 6.8.4. Management of On-target Off-tumor Toxicity

Examples of on-target off-tumor toxicities have been observed in different immunotherapies where these events were not expected from pre-clinical data. It is difficult to anticipate all “autoimmune inflammation” that theoretically may be induced by an on-target off-tumor effect of ELI-002. For that reason, Grade 3 or higher autoimmune toxicity is considered a DLT (ie, fits non-hematologic ≥Grade 3 toxicity; see [Section 6.7.3](#)) Any observed treatment emergent autoimmune events must be followed closely. The exact diagnostic and the therapeutic approach to be followed will be left to the investigator’s discretion who can contact at any time the Sponsor Medical Monitor. The Sponsor may discuss any specific case with the SMC members to evaluate appropriate therapeutic action.

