### **DLT definition:**

A DLT will be defined as any event at least possibly related to ELI-002 as follows:

- a. Any Grade  $\geq 3$  non-hematologic toxicity except asymptomatic laboratory abnormalities (see Protocol Section 12.2.1.1)
- b. Any Grade  $\geq 3$  toxicity involving major organ systems for greater than 72 hours and occurring within 28 days of subcutaneous administration
- c. Grade 3 CRS (Cytokine Release Syndrome) that does not resolve to  $\leq$  Grade 2 within 7 days
- d. Any Grade 4 CRS that does not improve to  $<$  Grade 2 within 72 hours
- e. Any Grade  $\geq 3$  autoimmune disorder
- f. Any Grade  $\geq 3$  rash that does not resolve to  $\leq$  Grade 1 within 7 days with appropriate treatment

The DLT observation period will be 28 days following first dose.

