**Table 7: Planned Summaries of Adverse Events**

AE Type \ Summarize by	Overall Summary [*]	By Cohort and Overall, SOC & PT	Additional Summary
TEAEs	X	X	By Cohort and Overall/Maximum CTCAE grade/SOC/PT By Cohort and Overall leading to study discontinuation
Serious TEAEs	X	X	By Cohort and Overall/relationship to study treatment/SOC/PT
Leading to study treatment discontinuation	X	X	By Cohort and Overall/relationship to study treatment/SOC/PT By Cohort and Overall/PT
Leading to death	X	X	
DLT (Phase 1A only) [#]	X	X	
Related TEAE	X	X	By Cohort and Overall/ leading to study discontinuation
Related TEAEs leading to study treatment discontinuation	X	X	
Cytokine Release Syndrome	X	X	
ICANS		X	
Reactogenicity event	X		By Reactogenicity type, events and toxicity grade

Note: all summary tables will be by Phase, Cohort/Overall.

**Final Analysis  
Statistical Analysis Plan (SAP)**

[\*] All types of AEs with “X” sign will be summarized in one overall summary table of TEAE, including outcome and action taken.

[#] Dose Limiting Toxicities (DLTs) are defined in the Protocol Section 6.7.3. The percentage of subjects having a DLT is based on all treated subjects in each cohort. DLT flag may be added to selected listings of adverse events as appropriate.

Where a subject has the same adverse event, based on PT reported multiple times, the subject will only be counted once at that PT level. Where a subject has multiple adverse events within the same system organ class, the subject will only be counted once at that SOC level.

Any AE with a missing severity based on CTCAE grading, or ASTCT in the case of CRS or ICANS, will be presented in the summary table under the category of “Missing” and will not be imputed. Any AE with a missing relationship to study treatment will be imputed as “Related”. Any AE with a missing “Serious” evaluation will be imputed as “Serious”.

For all AE data captured in the study by the Case Report Form (CRF), by-subject listings will be provided for all AEs, serious TEAEs, TEAEs leading to dose reduction or interruption, DLT and death, respectively.

Cytokine Release Syndrome, ICANS, and reactogenicity to the vaccine data captured in the CRF will be provided in a by-subject listing.

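### Protocol 6.7.3(a) and 12.2.1.3 give different answers on whether a related Grade 3 or higher injection-site reaction or pruritus is a DLT, and neither the protocol nor the SAP reconciles them

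*Protocol*

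**What the plan says.** **DLT definition.** Clause (a) of protocol 6.7.3 covers any Grade 3 or higher event judged at least possibly related, in the words "non-hematologic toxicity except asymptomatic laboratory abnormalities (see Section 12.2.1.1"). The synopsis has the same clause. SAP 8.1 repeats it: "non-hematologic toxicity except asymptomatic laboratory abnormalities (see Protocol Section 12.2.1.1"). None of the three mentions injection-site reactions or pruritus.

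**Reactogenicity.** Protocol 12.2.1.3 states: "Injection site reactions, skin rash, and pruritis will not be considered a DLT or safety event and should be recorded in the patient diary". It adds the reactogenicity eCRF as a place of record. It restores DLT status only for severe rashes of the Stevens-Johnson or toxic epidermal necrolysis kind. It then refers the reader to 6.7.3 without saying whether it limits that section or yields to it. Section 6.7.3 does not refer back.

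**Analysis.** The footnote to the adverse event summary table in SAP 13.7.1 says: "Dose Limiting Toxicities (DLTs) are defined in the Protocol Section 6.7.3". The same table plans a separate reactogenicity summary by type and grade. Nothing links the two.

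**Grading.** Protocol 12.2.1.1 and 12.4 use CTCAE v5 for adverse events. Protocol 12.5 says: "Reactogenicity will be assessed according to the toxicity grading scale for local reactions for preventive vaccines". It points to 12.2.1.3, where no scale is set out.

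**Use of the DLT definition elsewhere.** The dose hold in 6.7.1 applies to "Adverse event(s) that meet the definition of DLT caused by prior treatment". It sends the reader to 6.7.3 for the DLT and to 12.4 "for the definition of Common Terminology Criteria for Adverse Events (CTCAEs").

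**The concern.** Two sections of one protocol classify the same event differently, and the difference feeds a primary endpoint, the MTD. A site following 12.2.1.3 puts a Grade 3 injection-site reaction on the reactogenicity form as a non-DLT. A programmer following the SAP footnote goes to 6.7.3, where clause (a) read literally counts it. The study report's DLT count could then differ from the count the SMC used. The hold on that subject's next dose under 6.7.1 turns on the same question.

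The event class is the expected one for this product. Protocol 4.6.3 names injection-site reaction as the one adverse event so far attributed to ELI-002. In the three-month mouse study (protocol 4.4.1.2), local injection-site damage was the adverse finding at the high adjuvant dose. The SAP adds adjuvant cohorts of 5 and 10 mg. These are 5.0/2.5 = 2 and 10.0/2.5 = 4 times the top dose listed in the protocol.

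Skin rash is in similar tension. Clause 6.7.3(f) makes a Grade 3 or higher rash a DLT if it has not settled to Grade 1 or below within 7 days of appropriate treatment. Section 12.2.1.3 excludes rash apart from the severe kinds. The gap is narrower here, because a reader could treat any Grade 3 rash as severe.

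**Working it through.** The plan has no figure to reproduce: its sample size is explicitly not power-based. The check compares the texts and then runs the stated 3+3 rule without assuming any event rate.

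**Inputs.** Protocol 6.1.1 and SAP 8.1: 0 of 3, escalate; 1 of 3, expand to 6; 2 or more of 3, toxic; 1 of 6, next cohort may begin; 2 or more of 6, toxic. Protocol 6.7.3: the MTD is the highest dose with DLT incidence below 33%; the window is 28 days.

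**Definitions.** Let *m* be the number of subjects with some other DLT. Let *k* be the number of further subjects whose only candidate event is a related Grade 3 or higher injection-site reaction or pruritus.

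- Count under 6.7.3(a), read literally: *m* + *k*
- Count under the 12.2.1.3 exclusion: *m*

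| n | m | k | 6.7.3(a) | 12.2.1.3 | Call differs? |
|---|---|---|---|---|---|
| 3 | 0 | 1 | 1/3, expand | 0/3, escalate | yes |
| 3 | 0 | 2 | 2/3, toxic | 0/3, escalate | yes |
| 3 | 1 | 1 | 2/3, toxic | 1/3, expand | yes |
| 6 | 0 | 1 | 1/6 = 16.7%, may continue | 0/6, may continue | no |
| 6 | 0 | 2 | 2/6 = 33.3%, toxic | 0/6, may continue | yes |
| 6 | 1 | 1 | 2/6 = 33.3%, toxic | 1/6 = 16.7%, may continue | yes |

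Since 33.3% is not below 33%, 2/6 also fails the MTD definition. One such event can turn a dose from acceptable to toxic only if another subject has a different DLT; otherwise two are needed. A single event among the first three changes the next step (expand rather than escalate) but does not by itself make the dose toxic.

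**Is the information already collected?** Doses 1 to 4 fall on protocol days 57, 64, 71 and 78. Subtracting 56 gives study days 1, 8, 15 and 22. Each dose starts a 7-day diary, so 4 × 7 = 28 days. With visits on schedule, the diaries nominally cover the whole DLT window.

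**Why no probability is given.** The documents state no rate for these events, so any probability of a changed call would only reflect the rate chosen.

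**The case against.** The strongest reply is structural. Clause (a) cannot be a literal catch-all. If it were, the time limits in (c) and (d) for cytokine release syndrome and in (f) for rash would have no effect, because every related Grade 3 event would already be a DLT. Specific text must therefore be able to narrow (a). Section 12.2.1.3 is the specific text on injection-site reactions and cites 6.7.3 straight afterwards. Excluding expected local reactions from DLTs is also a legitimate choice for a vaccine.

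Much of this stands. It makes a deliberate exclusion plausible, and a reader who infers that 12.2.1.3 is simply a mistake goes further than the documents allow. It does not settle the matter. Clauses (c), (d) and (f) sit inside 6.7.3, and none concerns injection-site reactions. Section 6.8.4 uses (a) as a general category: "Grade 3 or higher autoimmune toxicity is considered a DLT", because it fits the non-hematologic clause. The SAP footnote takes its DLTs from 6.7.3 without carrying over any exclusion.

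Two further replies have weight. The SMC judges the totality of safety, so an excluded event was not hidden from it. The SAP also already plans reactogenicity by grade and a by-subject listing, so high-grade local reactions will be visible. That output still does not show whether any of them belongs in the DLT count.

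A reader might also infer that no scale is named or that nothing indicates which section applies. Neither holds: 12.5 names a vaccine scale, 12.2.1.1 and 12.4 name CTCAE v5, and the SAP directs its DLT table to 6.7.3. What is missing is a link from either scale to the DLT grade for these events, and a statement of which section governs escalation.

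**Conclusion.** The inconsistency is real and worth correcting in the reporting. Followed as written, the plan permits two DLT counts for the same data. Their difference ranges from no change of call (1/6 against 0/6) to a toxic dose against a clean one (2/6 = 33.3% against 0/6).

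The effect is conditional on related Grade 3 or higher injection-site reactions or pruritus (or, under the parallel tension, rash) occurring within 28 days of first dose. The documents report no such event. The SMC charter and the diary template were not available, and either may contain the rule or the scale.

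Two stronger conclusions might be drawn, and the documents support neither. One is that escalation decisions or the MTD were wrong; there is no evidence of that. The other is that only Grade 1–2 reactions were meant to be excluded. Section 6.8.5 speaks of routine reactions, which hints that way, but 12.2.1.3 says no such thing. The synopsis dates last enrolment to 2Q2023, so on that timetable the remaining value lies in an unambiguous DLT and MTD report.

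**What to change.** 1. State in the SAP or clinical study report which rule and which grading scale the SMC actually applied at the cohort reviews.
2. From the existing reactogenicity and adverse event eCRF data, list every Grade 3 or higher injection-site reaction, pruritus and rash within 28 days of first dose. If the reactogenicity form did not capture relatedness, treat the event as related, as SAP 13.7.1 does for adverse events with that field missing.
3. Report DLT counts by cohort, and the resulting MTD, side by side under 6.7.3 as written and under the 12.2.1.3 exclusion. If there were no such events, one sentence closes the point.
4. If the protocol is amended again, and in later protocols, align 6.7.3 with 12.2.1.3 and name the scale. Limiting the exclusion to Grade 1–2 is an option there. It should not be imposed retrospectively as the primary DLT definition, because that would redefine a primary endpoint after dosing.

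The cost is one statement, one listing and one small table from data already collected. The SAP revision history shows version 3.0 as an updated draft with the day in August 2024 left open. If it has since been finalised, the study report can carry the same material.
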